14.1 Ethical Standard

The investigator will ensure that this study is conducted in full conformity with the principles set forth in The Belmont Report: Ethical Principles and Guidelines for the Protection of Human Subjects of Research, as drafted by the US National Commission for the Protection of Human Subjects of Biomedical and Behavioral Research (April 18, 1979) and codified in 45 CFR Part 46 and/or the ICH E6.

14.2 Institutional Review Board

The protocol, informed consent form(s), recruitment materials, and all participant materials will be submitted to the IRB for review and approval. Approval of both the protocol and the consent form must be obtained before any participant is enrolled. Any amendment to the protocol will require review and approval by the IRB before the changes are implemented in the study.

14.3 Informed Consent Process

Informed consent is a process that is initiated prior to the individual agreeing to participate in the study and continues throughout study participation. Extensive discussion of risks and possible benefits of study participation will be provided to participants and their families, if applicable. A consent form describing in detail the study procedures and risks will be given to the participant. Consent forms will be IRB-approved, and the participant is required to read and review the document or have the document read to him or her. The investigator or designee will explain the research study to the participant and answer any questions that may arise. The participant will sign the informed consent document prior to any study-related assessments or procedures. Participants will be given the opportunity to discuss the study with their surrogates or think about it prior to agreeing to participate. They may withdraw consent at any time throughout the course of the study. A copy of the signed informed consent document will be protected by emphasizing to them that the quality of their clinical care will not be adversely affected if they decline to participate in this study. The consent process will be documented in the clinical or research record.

14.4 Exclusion of Women, Minorities, and Children (Special Populations)

Individuals age 18 years or older will not be excluded based on gender, race or economic status.

14.5 Participant Confidentiality

Participant confidentiality is strictly held in trust by the investigators, study staff, and the sponsor(s) and their agents. This confidentiality is extended to cover testing of biological samples and genetic tests in addition to any study information relating to participants.

The study protocol, documentation, data, and all other information generated will be held in strict confidence. No information concerning the study or the data will be released to any unauthorized third party without prior written approval of the sponsor.

The study monitor or other authorized representatives of the sponsor may inspect all study documents and records required to be maintained by the investigator, including but not limited to, medical records (office, clinic, or hospital) for the study participants. The clinical study site will permit access to such records.

14.6 **Future Use of Stored Specimens and Other Identifiable Data**

No residual specimens will be maintained after the study is complete.

15 Data Handling and Record Keeping

The investigators are responsible for ensuring the accuracy, completeness, legibility, and timeliness of the data reported. All source documents must be completed in a neat, legible manner to ensure accurate interpretation of data. The investigators will maintain adequate case histories of study participants, including accurate case report forms (CRFs), and source documentation.

15.1 Data Management Responsibilities

Data collection and accurate documentation are the responsibility of the study staff under the supervision of the investigator. All source documents and laboratory reports must be reviewed by the study team and data entry staff, who will ensure that they are accurate and complete. Unanticipated problems and adverse events must be reviewed by the investigator or designee.

15.2 Data Capture Methods

The study case report form (CRF) is the primary data collection instrument for the study. All data requested on the CRF must be recorded. All missing data must be explained. If a space on the CRF is left blank because the procedure was not done or the question was not asked, write "N/D". If the item is not applicable to the individual case, write "N/A". All entries should be printed legibly in black ink. If any entry error has been made, to correct such an error, draw a single straight line through the incorrect entry and enter the correct data above it. All such changes must be initialed and dated. DO NOT ERASE OR WHITE OUT ERRORS. For clarification of illegible or uncertain entries, print the clarification above the item, then initial and date it.

15.3 Types of Data

Safety, laboratory (clinical, pharmacokinetic, and pharmacodynamic), and outcome data will be recorded. Accrual data will be recorded and will be monitored quarterly by the MDG.

15.4 Study Records Retention

Study records will be maintained for at least three years from the date that the grant federal financial report (FFR) is submitted to the NIH.

Study documents must be retained for a minimum of 2 years after the last approval of a marketing application in an ICH region and until there are no pending or contemplated marketing applications in an ICH region or until at least 2 years have elapsed since the formal discontinuation of clinical development of the investigational product. These documents will be retained for a longer period, however, if required by local regulations. No records will be destroyed without the written consent of the sponsor, if applicable. It is the responsibility of the sponsor to inform the investigator when these documents no longer need to be retained.

15.5 **Protocol Deviations**

A protocol deviation is any noncompliance with the clinical study protocol, Good Clinical Practice, or Manual of Procedures requirements. The noncompliance may be on the part of the participant, the investigator, or study staff. As a result of deviations, corrective actions are to be developed by the study staff and implemented promptly.

All deviations from the protocol must be addressed in study participant source documents and promptly reported to the IRB and other regulatory bodies according to their requirements

16 Study Finances

16.1 Funding Source

This study will be funded by Pfizer, Inc and Thomas Jefferson University.

16.2 Conflict of Interest

Any investigator who has a conflict of interest with this study (patent ownership, royalties, or financial gain greater than the minimum allowable by their institution, etc.) must have the conflict reviewed by a properly constituted Conflict of Interest Committee with a Committee-sanctioned conflict management plan that has been reviewed and approved by the study sponsor prior to participation in this study. All Jefferson University Investigators will follow the TJU Conflicts of Interest Policy for Employees (107.03).

16.3 Participant Stipends or Payments

Participants will not receive payment for participation in the study.

17 Publication and Data Sharing Policy

This study will comply with the NIH Public Access Policy, which ensures that the public has access to the published results of NIH funded research. It requires scientists to submit final peer-reviewed journal manuscripts that arise from NIH funds to the digital archive PubMed Central upon acceptance for publication.

The International Committee of Medical Journal Editors (ICMJE) member journals have adopted a clinical trials registration policy as a condition for publication. The ICMJE defines a clinical trial as any research project that prospectively assigns human participants to intervention or

concurrent comparison or control groups to study the cause-and-effect relationship between a medical intervention and a health outcome. Medical interventions include drugs, surgical procedures, devices, behavioral treatments, process-of-care changes, and the like. Health outcomes include any biomedical or health-related measures obtained in patients or participants, including pharmacokinetic measures and adverse events. The ICMJE policy requires that all clinical trials be registered in a public trials registry such as ClinicalTrials.gov, which is sponsored by the National Library of Medicine. Other biomedical journals are considering adopting similar policies. The ICMJE does not review specific studies to determine whether registration is necessary; instead, the committee recommends that researchers who have questions about the need to register err on the side of registration or consult the editorial office of the journal in which they wish to publish.

U.S. Public Law 110-85 (Food and Drug Administration Amendments Act of 2007 or FDAAA), Title VIII, Section 801 mandates that a "responsible party" (i.e., the sponsor or designated principal investigator) register and report results of certain "applicable clinical trials:"

Trials of Drugs and Biologics: Controlled, clinical investigations, other than Phase I investigations, of a product subject to FDA regulation;

Trials of Devices: Controlled trials with health outcomes of a product subject to FDA regulation (other than small feasibility studies) and pediatric postmarket surveillance studies.

NIH grantees must take specific steps to ensure compliance with NIH implementation of FDAAA.

18 Literature References

Appendix A: Schedule of Events

Appendix B: ECOG Performance Status

Appendix C: Sample Handling, Processing, and Storage Instructions

Appendix D: Requesting a Dose Escalation/Expansion Approval

APPENDIX A: SCHEDULE OF EVENTS

	Baseline	Induction Day+1	Induction Day +4 ¹⁰	Induction Day +8	Induction Day +12 ¹⁰	Induction Days +14 and +21 ¹⁰	Induction Day +28 ¹⁰	Maintenance Cycle 1 (weekly)	Maintenance Day +28 ¹⁰ *	Maintenance Cycles 2-6 (every other week) ¹¹	Follow-up ^{7,8}
Informed Consent	X1										
Medical/Oncologic History	X1										х
Physical Examination (including neurological exam)	X ¹	x		x			x		X		
Vital Signs	X1	X		Х			X		х		
Performance Status	X1										
Review of concomitant medications	X1	x		x			x		x		x
Adverse Event Assessment		х		х			х		х		X ⁶
Laboratory Studies											
CBC with differential	X1	х	х	х	х	x	х	x	х	x	
Serum Chemistry, Electrolytes	X ^{1,7}	X ⁷	х	X ⁷	x	x	X ⁷	x	X ⁷	x	
Liver Function Tests	X1	х	х	х	х	x	х	x	x	x	
Pregnancy test	X ^{1,2}										
Pharmacokinetics		X ³		X ³							
Pharmacodynamics	X ³	X ³		X ³							
Tests & Studies											
Bone Marrow Biopsy/Aspirate ⁹	X ^{1,4}						x		x		X ⁵
Investigational Agent											
Pill Diary Given to Patient	X1										

Note: Palbociclib will be given with a one week lead-in starting on Day -7 to Day -1. *Patients who continue treatment for multiple cycles will have the maintenance Day +28 procedures repeated for each cycle.

- To be done within twenty-one days prior to first dose of study drug unless otherwise indicated (with exception to the bone marrow biopsy/aspirate which is required at any time prior to study treatment). Informed consent, baseline procedures, and confirmed eligibility must be completed prior to the one week lead in with Palbociclib (starting on Day -7)
- 2. Only perform for females of child bearing potential (serum or urine)
- 3. Blood to be drawn prior to administration of palbociclib and dexamethasone on day +1, and day +8. PK samples will be one tube of 3-4mL. PD samples are 10mL each.
- 4. The bone marrow aspirate may be replaced by 20 mLs of peripheral blood if the patient has a peripheral leukemic blast count ≥200/μl.
- 5. In patients who attain a CR, a bone marrow should ONLY be performed after cycle 1 maintenance if there is a suspicion/evidence of relapse based on peripheral blood studies or other clinical indications during the follow up period.
- 6. All AEs will be followed until resolution. Patients will be monitored for AEs for 30 daysafter the end of therapy or until initiation of a new anti-cancer therapy.
- 7. Serum chemistry and electrolytes labs should include: creatinine, BUN, glucose, magnesium, phosphate, and urate. Liver function labs should include: bilirubin, SGOT (AST), SGPT (ALT), alkaline phosphatase.
- 8. Patients will be followed for disease status until relapse/progression
- 9. Correlative studies will be performed by the [name] laboratory on peripheral blood or bone marrow.
- 10. Labs and bone marrow biopsy/aspirate may be performed ±2 days from the desired study day.
- 11. Patients who remain on maintenance for >6 months may have labs checked monthly.

APPENDIX B: ECOG PERFORMANCE STATUS

Grade	ECOG
0	Fully active, able to carry on all pre-disease performance without restriction
1	Restricted in physically strenuous activity but ambulatory and able to carry out work of a light or sedentary nature, e.g., light house work, office work
2	Ambulatory and capable of all self-care but unable to carry out any work activities. Up and about more than 50% of waking hours
3	Capable of only limited self-care, confined to bed or chair more than 50% of waking hours
4	Completely disabled. Cannot carry on any self-care. Totally confined to bed or chair
5	Dead

As published in Am. J. Clin. Oncol.:Oken, M.M., Creech, R.H., Tormey, D.C., Horton, J., Davis, T.E., McFadden, E.T., Carbone, P.P.: Toxicity And Response Criteria Of The Eastern Cooperative Oncology Group. Am J Clin Oncol 5:649-655, 1982.

APPENDIX C: SAMPLE HANDLING, PROCESSING, and STORAGE INSTRUCTIONS FOR PK and PD SAMPLES

Suggested Sample Handling, Processing and Storage Instructions for Palbociclib (PD-0332991):

Pharmacokinetics of Palbociclib

- Blood samples (3 or 4 mL, depending on the availability of the blood collection tube) to
 provide a minimum of 1.0 mL of plasma for pharmacokinetic analysis of Palbociclib will
 be collected into appropriately labeled¹ tubes containing dipotassium
 ethylenediaminetetraacetic acid (K₂EDTA) per time point.
- Upon collection of the blood PK samples, keep the samples on wet ice at all times prior to processing to plasma.
- The blood samples have to be processed to plasma and placed in a freezer at -20°C within 1 hour of collection.
- To process the blood samples to plasma, centrifuge the blood samples in a refrigerated centrifuge at approximately 4 °C at about 1700 x g for approximately 10 minutes.
- Using a clean separate pipette for each time point, transfer the plasma samples into prelabeled 4 or 5 mL polypropylene cryovials and store in the freezer at approximately -20°C until shipment. If a -20°C freezer is not available at the site the samples may be stored at -80°C. Palbociclib is stable at -20°C and -80°C for 439 days in frozen K₂EDTA plasma.
- Ship the frozen samples on dry ice to the contract bioanalytical laboratory.

¹ All information added to the labels should be written with an indelible marker; water-based inks will smear during thawing, making the label unreadable rendering the written information useless. Labels should be affixed only to DRY surfaces.

Labels should contain, at a minimum, the following information: -Protocol # or Pfizer IIR Tracking # -Investigator Name -Subject ID -Sample Matrix (e.g. plasma) -Analyte (e.g. palbociclib) -Visit (e.g. C1D15) -Nominal Sampling Time (e.g. 1Hr)

Sample Shipment

Contract bioanalytical laboratory contact and shipping address will be provided at a later date by email.

Laboratory Address: PPD Inc [name] [name] United States

Suggested Sampling, Handling, Processing, and Storage Information for PD Analyses

Pre-treatment and post-treatment peripheral blood and/or bone marrow samples (10 mL/each) will be collected in heparinized 10-ml green-top tubes and transported in ice to [name] laboratory ([name]). Samples will be immediately processed by removing red blood cells using an Ammonium Chloride solution (Stem Cell Technology). Then, mononuclear cells will be purified through Ficoll Hypaque centrifugation and subjected to FACS-sorting to isolate CD19+ B-cells. From these cells, we will obtain whole lysates for western blot analyses and total RNA for gene expression profiles (microarrays or RNA-Seq). Cell lysates and RNAs will be stored at -70 degrees. We anticipate that we will obtain enough cells (ideally, 5-10 x 10^6 cells/sample) to extract proteins and RNA. If the number of CD19+ cells is insufficient, we will give priority to the preparation of whole cell lysates for western blot analyses of palbociclib and dexamethasone response biomarkers.

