1.2 Rationale for the Proposed Study

This study will evaluate the use of palbociclib in conjunction with dexamethasone for the treatment of relapsed or refractory ALL. We will begin giving palbociclib at a dose of 100mg PO daily with escalation in increments of 25mg to a maximum dose of 150mg. Initial Phase I testing of palbociclib in patients with advanced solid tumors revealed a maximum tolerated dose (MTD) of 125mg daily. The primary dose limiting toxicity was bone marrow suppression, an important consideration when treating sold tumors, but an expected, and possible surrogate marker for efficacy, in the treatment of leukemia. Dexamethasone may decrease serum drug levels of palbociclib, so we will begin with a palbociclib dose of 100mg and escalate from there. Dosing regimens in ALL vary; in this study, we propose giving dexamethasone at a starting dose of 20mg daily in conjunction with palbociclib, and then decreasing the dose by 4mg weekly over 4 weeks to minimize side effects.

If the combination of palbociclib and dexamethasone is found to be safe and well-tolerated, we would hope to move forward with a larger, Phase II study.

1.3 **Correlative Studies**

The following correlative studies will be performed in the [name] Laboratory:

- 1. RB phosphorylation (CDK4/6 phosphorylation sites) by Western blot as the primary read-out of palbociclib activity.
- 2. FOXM1 expression by Western blot as the secondary read-out of palbociclib activity (since FOXM1 is a CDK4/6 target)

- 3. RNA isolated from CD19+ cells will be used for gene expression profiles (microarray or RNA-Seq) to measure p21 expression as an indicator of cell cycle activity
- RNA isolated from CD19+ cells will be used for gene expression profiles (microarray or RNA-Seq) to measure S-Phase, Annexin V/Caspase 3 activation as indicators of proliferation and apoptosis
- RNA isolated from CD19+ cells will be used for gene expression profiles (microarray or RNA-Seq) to measure Expression of Myb and Bcl-2 as a read-out of dexamethasone sensitivity

These analyses will be performed on pre-treatment samples (peripheral blood and/or bone marrow) as well as on day +1 (after 1 week of palbociclib alone) and day +8 (after 1 week of combined therapy) of treatment (peripheral blood).

1.4 **Potential Risks and Benefits**

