2.1.2 Secondary

• To evaluate the activity of palbociclib in combination with dexamethasone in patients with relapsed or refractory B-Cell ALL

2.1.3 **Exploratory**

- To determine the pharmacokinetic properties of palbociclib both alone and in combination with dexamethasone
- To measure the on-target effects of palbociclib
- To measure the on-target effects of dexamethasone
- To measure cell cycle activity
- To evaluate cellular proliferation and apoptosis

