2.2.3 Exploratory

- To evaluate a number of pharmacokinetic and pharmacodynamic biomarkers that measure the effect of the combination of palbociclib and dexamethasone including:
 - Plasma levels of palbociclib
 - Western blots of phospho-RB (using antibodies that recognize CDK4/6 phosphorylation sites on RB) and FOXM1 (CDK4/6 substrate which is stabilized by phosphorylation) on lysates from peripheral blood or bone marrow CD19+ cells (obtained by FACS sorting).
 - RNA isolated from CD19+ cells will be used for gene expression profiles (microarray or RNA-Seq) to measure Myb and Bcl-2 levels
 - RNA isolated from CD19+ cells will be used for gene expression profiles (microarray or RNA-Seq) to measure levels of p21, CDK2, and cyclin E as markers of cell cycle activity
 - RNA isolated from CD19+ cells will be used for gene expression profiles (microarray or RNA-Seq) to measure levels of S-Phase and Annexin V/Caspase 3 activation as indicators of proliferation and apoptosis

3 Study Design

This single arm, Phase I, single institution, dose escalation study will follow a traditional 3+3 design (See Section 11).Patients who are receiving treatment with steroids at the time of enrollment must undergo at least a 24 hour washout period prior to their first dose of palbociclib.

Patients will receive a 1-week lead-in (Day -7 to Day -1) of palbociclib alone at the appropriate dose level. This will be followed by induction with 4 weeks of palbociclib in combination with dexamethasone. Patients will receive dexamethasone 20mg daily from days 1-7, 16mg daily from days 8-14, 12mg daily from days 15-21, and 8mg daily from days 22-28. If a patient experiences a DLT as defined in section 6.2.1, the patient will stop the study drugs and come off of the trial. At the completion of induction therapy (Day +28), a bone marrow biopsy will be performed. If the marrow is hypoplastic (<10% cellularity), further treatment will be held (up to 4 weeks from the last day of the induction cycle) to await count recovery. Count recovery will be defined as \geq 10% cellularity in the bone marrow, neutrophils \geq 0.75 x10⁹/L, and a platelet count \geq 75 x 10⁹/L. At the time of count recovery a repeat bone marrow biopsy will be performed. If a CR, CRi, PR, or SD is seen, the patient will move to maintenance therapy.

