4.1 Eligibility Criteria

4.1.1 Inclusion Criteria

Individuals must meet all of the following inclusion criteria in order to be eligible to participate in the study:

1. Patients must have histologic evidence of relapsed or refractory B-cell ALL

- 2. Patients must be ≥18 years of age
- 3. Patients must have an ECOG performance status of 2 or less (see Appendix B)
- 4. Ph+ patients must be refractory to or intolerant of standard tyrosine kinase inhibitor therapy.

5. Patients must be able to consume oral medication.

6. Patients must have recovered to \leq Grade 1 or stabilized from the toxic effects of any prior chemotherapy (except alopecia).

7. Required initial laboratory values: $CrCL \ge 60mL/min/1.73m^2$ calculated by Cockroft-Gault; total bilirubin <1.5xULN; negative serum or urine pregnancy test for women with child-bearing potential.

8. Patients must be able to sign consent and be willing and able to comply with scheduled visits, treatment plan, procedures, and laboratory testing. When it is determined by the study investigator that a potential research participant is cognitively impaired, a surrogate consent from a caregiver or legally-authorized representative will be obtained. Caregiver or legally-authorized representative will ensure that they comply with the protocol in order for the subject to be considered eligible.

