7.2.2 Special Assays or Procedures

Plasma levels of palbociclib for will be determined by a validated assay performed at PPD in Richmond, VA. See Appendix C for full instructions on sample storage, handling, and processing for PK/PD analysis. Palbociclib levels will be obtained **within 1 hour prior** to dosing with dexamethasone and palbociclib on days +1 and +8 of induction.

For analyses of molecular markers of palbociclib and dexamethasone response, we will perform western blots of phospho-RB (using antibodies that recognize CDK4/6 phosphorylation sites on RB) and FOXM1 (CDK4/6 substrate which is stabilized by phosphorylation) on lysates from peripheral blood or bone marrow CD19+ cells (obtained by FACS sorting). We will also assess levels of p21, cyclin E, and CDK2 as markers of cell cycle activity.

As markers of Dexamethasone response, we will assess MYB and BCL2 levels in pre-treatment and post-treatment (palbociclib and dexamethasone combination) CD19+ peripheral blood or bone marrow cells.

For analyses of additional markers of drug response, RNA will be isolated from pre-treatment and post-treatment CD19+ cells and used for gene expression profiles (microarray or RNA-Seq).

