All criteria for CR are satisfied except there are between 5% and 25% lymphoblasts in the bone marrow

Stable Disease (SD)

Failure to achieve at least a PR, but with no evidence of progression as defined as an increase of peripheral blood or bone marrow blasts of more than 10% from nadir during study.

Progressive Disease (PD)

For patients with < 5% blasts at baseline, there must be an increase to \ge 10% blasts. For patients with 5% to 10% blasts at baseline, there must be a \ge 50% increase to > 10% blasts.

For patients with 10% to 20% blasts at baseline, there must be a \ge 50% increase to \ge 20% blasts.

Response rate defined as the proportion of patients who achieve a CR, CRi, PR, or SD response will be estimated along with a 95% confidence interval.

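### Exploratory marker assays pool all CD19+ cells without recording the leukemic share, so a change in cell mix can look like a drug effect

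*Combined protocol and SAP*

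**What the plan says.** Appendix C describes the pharmacodynamic work-up: "mononuclear cells will be purified through Ficoll Hypaque centrifugation and subjected to FACS-sorting to isolate CD19+ B-cells". It continues: "From these cells, we will obtain whole lysates for western blot analyses and total RNA for gene expression profiles". The exploratory endpoints in section 2.2.3 name the same population for the Western blots, "on lysates from peripheral blood or bone marrow CD19+ cells (obtained by FACS sorting"), and sections 1.3 and 7.2.2 also work from CD19+ cells.

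The results are to be read as drug effects. Section 2.1.3 lists "To measure the on-target effects of palbociclib" as an objective, with a parallel one for dexamethasone. Section 7.2.2 opens: "For analyses of molecular markers of palbociclib and dexamethasone response, we will perform western blots of phospho-RB". On timing, section 1.3 says: "These analyses will be performed on pre-treatment samples (peripheral blood and/or bone marrow) as well as on day +1", followed by day +8, with both on-treatment samples taken from blood. Section 11.4 plans descriptive summaries only.

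The one contingency for the sort, in Appendix C, covers too few CD19+ cells, not too few leukemic ones. The blast threshold of 200/µL in section 6.1 and Appendix A governs only whether blood may replace the baseline marrow. No blast requirement applies to the day +1 or day +8 blood.

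**The concern.** CD19 marks the B lineage, and Appendix C itself calls the sorted product B-cells rather than blasts. A bulk assay on that pool returns an average over leukemic and normal cells. The average moves if a drug changes the cells, and also if the mix changes.

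The documents make a change in mix plausible:

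- Section 6.1 treats steroids as cytoreductive, and the interval from day +1 to day +8 is a week of dexamethasone plus palbociclib.
- Section 6.1 also allows hydroxyurea or steroids during screening, and Appendix A (note 1) lets the baseline marrow be taken at any time before study treatment. The mix may therefore shift before the first study dose.
- Baseline may be marrow while the later samples are blood, so the compartment can change along with treatment.

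For MYB the direction would flatter the drug. Section 1.1 describes c-Myb as highly expressed in immature hematopoietic cells and describes dexamethasone as lowering it. If mature normal B-cells replaced blasts, pooled MYB would be expected to fall in the same direction.

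The ambiguity may not be resolvable afterwards. Appendix C stores only lysates and RNA, and section 14.6 keeps no residual specimens once the study is complete.

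**Working it through.** The plan states no figure on this point, and section 11.1 tests no hypothesis, so there is nothing to reproduce. Two illustrations show the size.

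**1. Apparent change with no drug effect.** Let f be the leukemic share of the sorted CD19+ cells and r the marker level of a normal B-cell relative to a leukemic cell (set to 1). Both cell types keep constant levels.

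Pooled level = f + (1 - f) × r

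Apparent change = [f₁ + (1 - f₁)r] / [f₀ + (1 - f₀)r] - 1

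Both f and r are assumptions; the documents give neither.

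Share falling from 0.95 to 0.50:

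- r = 0: 0.95 to 0.50, or -47%
- r = 0.25: 0.9625 to 0.625, or -35%
- r = 0.5: 0.975 to 0.75, or -23%
- r = 1: 1 to 1, or 0%
- r = 1.5: 1.025 to 1.25, or +22%

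Share moving only from 0.95 to 0.90:

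- r = 0: 0.95 to 0.90, or -5%
- r = 0.5: 0.975 to 0.95, or -3%
- r = 1.5: 1.025 to 1.05, or +2%

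**2. What blast counts such shares imply.** With B blasts/µL and N normal B-cells/µL, f = B/(B + N). N is assumed to lie between 10 and 200/µL.

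- N = 10: 200 blasts/µL gives 200/210 = 0.95; 90 gives 90/100 = 0.90; 10 gives 10/20 = 0.50.
- N = 200: 200 blasts/µL gives 200/400 = 0.50.
- At 2,000 blasts/µL, f is 2,000/2,010 = 1.00 (N = 10) to 2,000/2,200 = 0.91 (N = 200).

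So with few normal B-cells, more than halving the blast count (200 to 90/µL) hardly matters, while a twenty-fold fall (200 to 10/µL) matters a good deal. With a high count throughout, the effect is small.

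**3. Yield, which bears on the remedy.** Appendix A sets pharmacodynamic samples at 10 mL, and Appendix C hopes for 5-10 million cells. At the 200/µL threshold, 10 mL holds 200 × 10,000 = 2.0 million blasts. Reaching 5-10 million from 10 mL needs 500-1,000 CD19+ cells/µL at full recovery.

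**The case against.** The strongest reply has five parts.

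- **Consequence.** The endpoints are exploratory and descriptive. This stands, and it limits the point to a minor one.
- **Timing.** The last marker sample is day +8, about two weeks after palbociclib starts, and the day +28 marrow is not a scheduled pharmacodynamic sample. The documents give no clearance rate, so a large fall in share within the window is possible but not shown. This stands, and the point is therefore conditional.
- **An existing check.** A CBC with differential is drawn at baseline, day +1 and day +8, so the blood blast burden is available beside each blood marker result. It would therefore be too strong to say that the two explanations can never be told apart. But the differential does not give the composition of the sort, and section 11.4 does not call for it to be used.
- **Self-limiting yield.** With 10-200 normal B-cells/µL, a sample that reaches the hoped-for yield is between (500 - 200)/500 = 60% and (1,000 - 10)/1,000 = 99% leukemic. This helps the better samples only; Appendix C still sends low-yield samples to Western blot.
- **Suggested handling.** Appendix C presents its handling as suggested, so the laboratory could add markers. Nothing in the plan asks it to.

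**Conclusion.** The point holds in conditional form. Followed as written, the plan can present a shift in cell mix as a marker response, because the sort is defined by CD19 alone and its leukemic share is neither recorded nor used. The bias needs two things together: a material change in that share, and a marker level that differs between normal and leukemic B-cells. Under the assumed ranges it runs from -47% to +22%, vanishes at equal marker levels, and is about 5% or less if the share stays between 0.90 and 0.95. DLT, MTD and response are untouched.

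A reader might infer more than the documents support:

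- That a composition change will be reported as a drug effect. No document gives the share, its change or the marker ratio, and the sign can go either way.
- That section 2.1.3 states its on-target objectives as effects in leukemic cells. It does not say so; that is a fair inference from the disease under study.
- That low-blast patients are expected, because section 11.2 has a row beginning "For patients with < 5% blasts at baseline". That row is part of a definition of progression, not a forecast of enrolment.
- That the sort would miss CD19-negative disease. Section 4.1.1 asks only that "Patients must have histologic evidence of relapsed or refractory B-cell ALL", without mentioning CD19, but nothing in the documents suggests that such patients will enrol.

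**What to change.** In Appendix C, record the leukemic (blast) percentage of every CD19+ sort at baseline, day +1 and day +8, by adding each patient's diagnostic blast markers to the existing sort panel.

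In section 11.4, report each patient's marker change beside that percentage, the sample compartment, and the blood blast count from the differential drawn at the same visit. Describe a change as on-target only where the leukemic share is stable, or after a sensitivity summary that accounts for it, for instance by setting the observed change beside the change that the mixture formula gives from share alone over a stated range of r.

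Blast-gated sorting may be used where yield allows but should not be mandatory: 2.0 million blasts in 10 mL at 200/µL is already below the 5-10 million hoped for. Samples should not be excluded on their on-treatment blast percentage, because that would remove the patients whose blasts cleared and tilt the summary toward those whose blasts did not.

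The cost is a few antibodies per sort, some work to match them to each patient, and one more column in the listings. No dose, visit or blood draw changes.
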